### Statistical analysis

We shall first assess the baseline association between androgens, insulin, and several measures of adiposity including body mass index, waist circumference and (in a sample of cases) percentage body fat, with Spearman correlation coefficients. We shall then compare the change in food consumption, body weight, and geometric means of hormone end points from baseline to 12 months in the intervention and control group.

The main analysis of the intervention effect on the incidence of recurrences will be by intention to treat, i.e. based on assigned treatment at the time of randomization, regardless of adherence. As a secondary analysis we shall assess the effect by change in body weight and biomarkers. We shall compute total survival, disease free survival and relapse free survival.

Hazard ratios and confidence intervals will be computed by the Cox proportional hazard model, with standard clinical-pathological prognostic covariates as potential confounders. Separate analyses will be carried out by ER, PR and erbB2 status. Interim analyses will be carried out as soon as the total follow-up person-years reach 2,500 (corresponding to  $\alpha$  =0.10 and  $\beta$ = 0.20 for a 33% reduction of recurrence rate).

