### Compliance

Compliance will be monitored through lifestyle compliance questionnaires, dietary questionnaires, weight change and plasma glucose, triglycerides, cholesterol, insulin, testosterone changes after one year of intervention. As adjuvant treatment may alter these biomarkers' level and confound the effect of the intervention, we shall compare blood samples collected in the same treatment phase: at least 3 months after the end of chemotherapy, if any, and 3 months after the start of hormonal therapy, if any, and one year later.

Altering the proportion of energy from dietary carbohydrate and fat has been shown to affect plasma lipid concentrations in controlled feeding studies. As we recommend to obtain carbohydrates from low glycemic index food, however, we do not expect any increase in

triglycerides. We expect a substantial reduction of total and LDL cholesterol and fasting glycaemia, minor changes in HDL cholesterol and triglycerides, and a substantial reduction of body weight and waist circumference in the intervention group compared with the control group. Total cholesterol change is an estimate of saturated fat intake change. Testosterone and insulin are also expected to decrease in subsequent samples, which will be assayed in the same batch. A compliance score will be computed, based on the direction of change in all these biomarkers.

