### **Control of potential biases**

Selection bias: the randomization will be carried out blindly, without any possibility of changing the allocation, within strata of age, date of diagnosis, treatment allocation (depending on stage and hormone receptor status) and number of positive axillary nodes at diagnosis (none, 1-3, 3 or more). Performance bias: patients will be recruited after the main treatments have been planned or delivered. In no case the allocation to the intervention or control group or the compliance will affect treatment.

Measurement bias: patients and researchers cannot be blinded, but the ascertainment of outcome will be carried out by clinicians that are not involved in the study. Attrition bias: Based on previous studies we expect a fairly high compliance in the intervention

group (>90%) but also some modification in the control group. After the main analysis by intention to treat, therefore, secondary analyses will be carried out by compliance score. Milestones and timing:

 $1^{st}$ )

3rd Month:  $2^{nd}$ ) 12th Month: 16th 3rd) Month:

testosterone by 10% or more and serum glucose and insulin by 5% or more in at least 50% of participants.

Operative study protocol and information system

Recruitment of at least 300 patients in the first year.

Compliance evaluation. The aim is to decrease serum cholesterol and

4th) 24th Month: Test of follow-up procedures and comparison of observed and expected number of recurrences

5th) 35th Month: First outcome analysis

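### The recurrence analyses by marker change and compliance score have no stated start of follow-up, and the 12-month comparison of arms has no stated baseline adjustment

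*Combined protocol and SAP*

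**What the plan says.** The Statistical analysis section makes intention to treat the main analysis of recurrence and then adds: "As a secondary analysis we shall assess the effect by change in body weight and biomarkers". The section Control of potential biases, under attrition, says that "secondary analyses will be carried out by compliance score". The Cox model is named in general terms ("Hazard ratios and confidence intervals will be computed by the Cox proportional hazard model"), with clinical-pathological covariates.

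The Compliance section defines the classification: "A compliance score will be computed, based on the direction of change in all these biomarkers". The changes it draws on include "insulin, testosterone changes after one year of intervention". To avoid confounding by adjuvant treatment, paired samples must come from the same treatment phase: at least 3 months after the end of chemotherapy, or "3 months after the start of hormonal therapy, if any, and one year later". Where this rule delays the first sample, the score falls later than one year after entry.

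For the biomarkers, the Statistical analysis section sets the two arms against each other: "We shall then compare the change in food consumption, body weight, and geometric means of hormone end points from baseline to 12 months". It names no model and no baseline covariate for that comparison.

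No section gives a time origin, a landmark or a time-dependent covariate for the analyses by score or marker change, or a rule for women without a score.

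**The concern.** **Start of follow-up.** A classification that becomes known at one year cannot safely label follow-up time before that point. If women with an early recurrence tend not to be scored, the scored women have a first year that is event-free by selection. Counting that year from randomization flatters them against any group that keeps its first-year events. The clinical-pathological covariates in the Cox model do not remove this. The result would matter because the plan offers the compliance analysis as its answer to expected lifestyle change in the control group, so it would be read alongside the primary result. The effect hoped for is a 25-33% reduction, so an artefact of similar size could be mistaken for support.

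**Baseline adjustment.** Comparing change between randomized arms is unbiased when the baseline precedes randomization, but it is less precise than adjusting for the baseline value. What is at stake is precision, not validity.

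**Working it through.** **Plan's own figures.** Statistical power section: 30% of 1,200 women with an event in 5 years, 0.30 × 1,200 = 360. The documents give no figure for the secondary analyses.

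**Inputs.** Five-year risk 30%, so cumulative hazard −ln(0.70) = 0.3567. Two time patterns are used: constant hazard, and the yearly shape of Table 4 (3.4, 4.7, 5.1, 4.7, 2.1; sum 20.0). Table 4 is used for shape only, since its rates are for all patients and for relapse alone. Assumptions not in the documents: every score falls at 12 months, Table 4 years are years since randomization, there is no dropout, the score is unrelated to risk, and women with a first-year event are not scored.

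**Events before the score.**
- Constant hazard: 0.3567/5 = 0.0713; 1 − exp(−0.0713) = 0.0689; × 1,200 = 83 (23% of 360).
- Table 4 shape: 0.3567 × 3.4/20.0 = 0.0606; 1 − exp(−0.0606) = 0.0588; × 1,200 = 71 (20%).

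**Comparison A: scored women against all controls, clock at randomization.** Rates are events over person-years, per woman randomized.
- Constant: scored 0.2311/4.1715 = 0.0554; controls 0.3000/4.2055 = 0.0713; ratio 0.78.
- Table 4 shape: scored 0.2412/4.1426 = 0.0582; controls 0.3000/4.1717 = 0.0719; ratio 0.81.

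**Comparison B: compliers against the rest, unscored women counted as non-compliers, half of scored women assumed to comply.** The compliers' rate is that of scored women. The rest have all remaining events and person-years.
- Constant: rest (0.3000 − 0.1156)/(4.2055 − 2.0857) = 0.0870; ratio 0.0554/0.0870 = 0.64.
- Table 4 shape: rest (0.3000 − 0.1206)/(4.1717 − 2.0713) = 0.0854; ratio 0.0582/0.0854 = 0.68.

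Large simulated Cox fits agree to about 0.01: 0.77 and 0.81 for A, 0.63 and 0.68 for B.

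**Sensitivity to who is scored** (rate ratios, constant / Table 4 shape):

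| Women with a first-year event who are still scored | A | B |
|---|---|---|
| none | 0.78 / 0.81 | 0.64 / 0.68 |
| half | 0.89 / 0.91 | 0.80 / 0.83 |
| all | 1.00 | 1.00 |

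If scored women are compared only with each other, or follow-up starts at the score, the ratio is 1.00 in every row.

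**Baseline adjustment.** With equal variance s² at both times and correlation r, the change has variance 2s²(1 − r) and the covariance-adjusted value s²(1 − r²). The ratio is (1 + r)/2, a reduction of (1 − r)/2: 5% at r = 0.9 and 25% at r = 0.5. The documents give no correlation, so this range is an assumption.

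**The case against.** The strongest reply is that the plan never proposes comparison A or B. The stated reason for the compliance score is that controls will also change, which points to scoring both arms; blood collection about every 12 months and yearly questionnaires support that. An analysis by measured change needs a measured change, so the natural comparison is among scored women, where the ratio is 1.00. Nor do the documents say that sampling stops at an event: local recurrence and a new primary are events, and such women could still attend. All of this stands. A reader might infer that the plan builds in an immortal-time artefact of the sizes in A and B; the documents do not support that. What remains is that they do not exclude it either.

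A reader might also infer that the change comparison is biased because women were selected for high testosterone or insulin. It is not: regression to the mean acts on both arms alike when the baseline precedes randomization.

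It is tempting to use the same-phase sample as the baseline covariate. For women recruited at diagnosis that sample may follow the start of intervention, and adjusting for it would remove part of the effect. For illustration, if half the effect is already present and the slope is 0.5 to 0.9, the share recovered is 1 − 0.5 × slope, or 75% down to 55%.

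Finally, the precision gain may be only about 5%, and an operative protocol is listed among the milestones where these details could be settled. Both are fair, and neither is a reason to leave the choices unwritten.

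**Conclusion.** The point holds as an omission in secondary analyses. The plan classifies women by something known only about a year after the baseline sample, when 20-23% of expected events may already have occurred, and leaves the time origin and the handling of unscored women open. The hazard ratios of about 0.77-0.81 and 0.63-0.68 show what the worst handling would produce under the stated assumptions. They are not predictions, and they shrink to 1.00 as more women with early events are scored. The missing baseline adjustment is a milder matter of precision. Neither part affects the intention-to-treat analysis of recurrence or the sample size. Even a correctly timed analysis by score remains a non-randomized comparison.

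**What to change.** **Recurrence by score or marker change.** Start follow-up at each woman's score sample, include only women event-free at that time, keep the prognostic covariates already planned, and label the result non-randomized. State that women without a score are left out and report their number by arm. The cost is the loss of events before the score, in this secondary analysis only: 71-83 if all scores fall at 12 months, and more if they fall later. As an upper illustration with all scores at 18 months:
- Constant hazard: 1,200 × (1 − exp(−1.5 × 0.0713)) = 122.
- Table 4 shape: 1,200 × (1 − exp(−(0.0606 + 0.5 × 0.0838))) = 117, where 0.0838 = 0.3567 × 4.7/20.0.

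**12-month comparison.** Compare weight and log biomarkers between arms by analysis of covariance with the pre-randomization value as covariate. That value is available because eligibility depends on a recruitment sample. Where the same-phase sample was taken after randomization, do not use it as the covariate in the main comparison; report change from it only as a supplementary analysis. This needs no new samples.

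Both changes are wording in the analysis plan and should be made before outcomes are examined.

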We now propose a randomized dietary and physical activity intervention trial to reduce BC recurrences (local, distant, or second BC) in BC patients at high risk because of high serum testosterone (>0.4 ng/ml), or insulin (>50 pmol/L), or the presence of metabolic syndrome. In these patients the estimated 5-year cumulative recurrence rate is 30%. Participants will be recruited through hospitals, patients' associations, and the media. We plan to recruit 1,200 patients and to randomize them in two groups: 600 shall receive standard recommendation for healthy lifestyle without, however, any active support; 600 shall receive a combination of individual and group contacts over the course of one year, including kitchen courses, gym and dance classes, common meals and reinforcing meetings, with emphasis on a comprehensive dietary change including low saturated fat and low refined carbohydrates, and high whole grain cereals and pulses consumption. Compliance will be monitored through weight change and plasma glucose, triglycerides, cholesterol and testosterone.

The main analysis will be by intention to treat. Under the hypothesis of reducing recurrence rate by 25% or 33% the statistical power of the study is 80% or, respectively, 90%, (P<0.05, 5-year follow-up).

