#### Insulin and related metabolic factors effect BC risk

Overweight and sedentary lifestyle are associated with insulin resistance. Women who gain weight in adulthood and overweight postmenopausal women have a greater risk for BC than lean women (11, 12). Postmenopausal women who engage in regular exercise (> 3 hours per week) have a reduced risk for BC compared with inactive women (13, 14). Several epidemiological studies found that high serum insulin and IGF-I levels are associated with increase BC risk (15-20), with, however, some inconsistencies as for the effect modification of age and menopausal status.

Insulin and testosterone effect prognosis in BC patients

In BC patients, high serum levels of insulin (21) and testosterone (22 and Micheli et al, submitted) are significantly associated with increased risk of recurrences; after adjustment for traditional prognostic factors (cancer stage at diagnosis, ER and PR) the RRs for BMI and for insulin in the upper quartile were about 2, while the RRs for testosterone in the upper tercile ranged from 2 to 7. We also found a borderline significant association of ER+ cancer with serum levels of estradiol, which, however, disappeared upon adjustment for testosterone levels (22). Testosterone levels are higher than estradiol levels, are easier to measure reproducibly and have lower intra- individual variability (23-25). For this reason, and because it proved to be predictive at any age, we chose testosterone as the main hormonal indicator of BC risk.

We also showed an high risk of recurrence in patients with metabolic syndrome, defined as the presence of three or more of the following factors: abdominal obesity (waist circumference >88 cm), hypertension (SBP>130 and /or DBP >85), hyperglycemia (>110mg/100ml), high triglycerides (>150 mg/100ml) or low HDL cholesterol (<50 mg/100ml) (26) (Table 1). Consistently, several observational studies suggested that sedentary habits (28) and overweight (27) are associated with increased BC incidence and BC recurrences.

Table 1. Hazard ratio of developing recurrences during 5.5-year follow-up of 110 BC patients according to the presence or absence of metabolic syndrome and serum testosterone levels above or under the median value (26).

Metabolic	Testosterone	Recurrence		Hazard	95% C.I
syndrome	>0.40 ng/ml	Yes	No	Ratio	
No	No	7	46	1	
Yes	No	1	3	2.2	0.2-19.4
No	Yes	17	24	3.8	1.5-9.5
Yes	Yes	7	5	6.7	2.3-19.8

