#### Study aims and design

We propose a randomized intervention trial of diet and physical activity to reduce BC relapse (local, distant), and second ipsilateral or contralateral BC, in BC patients at high risk of recurrence because of biochemical markers of increased risk, namely high serum testosterone and/or high fasting insulin and/or metabolic syndrome. Several other markers of increased recurrence risk are available, such as cancer stage at diagnosis, histological grade, hormonal receptors and other gene expression profile. All these will be registered, but we are specifically interested in markers of the host that can be modified through life-style.

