#### **Statistical power**

The survival of BC patients in Italy is dramatically increasing: 5-year relative survival increased from 80.6% for patients diagnosed in the early 1990s (Berrino et al, EUROCARE-3) (45) to 85.6% for patients diagnosed in the early 2000s (EUROCARE-4, unpublished). For these patients the estimated relapse free survival is 81.9 (EUROCARE high resolution study, unpublished). Such a survival improvement is accompanied by a postponement of the incidence of relapse (table 4). *Table 4. incidence rate of local + distant recurrences (EUROCARE, unpublished)* 

Follow-up year	relapse rate %	95% confidence interval
1 st	3.4	2.0 -5.8
$2^{nd}$	4.7	3.0-7.5
3 rd	5.1	3.2-8.1
4 th	4.7	2.9-7.8
5 th	2.1	0.9-4.6
$6^{\text{th}}$ to $8^{\text{th}}$	2.2	1.4-3.0

Based on EUROCARE data we estimate that the 5-year distant recurrences plus second ipsilateral or contralateral BC for patients recruited in the first few years after diagnosis will be about 20%. In the subgroup of patients selected on the basis of high insulin and/or testosterone levels (50% of cases with RR of the order of 3), we estimate that about 30% of patients will develop a recurrence or a second primary BC within 5-year follow-up: 360 cases out of 1200. Considering that the WINS randomized study obtained a 24% reduction of recurrence rate changing a single dietary factor (total fat) (39), and that observational studies suggested that a moderate physical activity may reduce recurrence rate by over 40% (28), we hypothesize that a comprehensive dietary intervention plus physical activity will reduce BC recurrence rate by 33% or more, but we consider also a more prudent estimate of 25% reduction.

The following table gives the number of patients (per arm) that we should recruit in order to have 90% or 80% power to detect a significant difference with  $\alpha < 0.05$ , two sided, or one sided ( $\alpha < 0.10$ ).

Power (1-β)	0.9	0.9	0.8	0.8
α	0.05	0.10	0.05	0.10
33% reduction	412	339	313	251
25% reduction	748	614	566	451

Our aim is to recruit 1,200 high risk patients in order to have 600 patients per arm, which shall guarantee 80% chance of getting a significant difference also with 25% reduction, and allowing for 90% compliance in the intervention group and 10% contamination of the control group.

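### The Cox model does not name baseline testosterone, insulin or metabolic syndrome as covariates; pre-specifying them would bring a modest gain in power at almost no cost

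*Combined protocol and SAP*

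**What the plan says.** The Statistical analysis section specifies the model in one sentence: "Hazard ratios and confidence intervals will be computed by the Cox proportional hazard model, with standard clinical-pathological prognostic covariates as potential confounders". The covariates are not listed, and the section does not say whether this or an unadjusted model is the primary test. It uses biomarkers elsewhere: for baseline correlations, for 12-month change, and for a secondary analysis by change.

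The background section on insulin and related metabolic factors turns to prognosis in breast cancer patients. After adjustment for stage, ER and PR it gives a relative risk of about 2 for insulin in the upper quartile, and for testosterone it states that "the RRs for testosterone in the upper tercile ranged from 2 to 7". Table 1 in the same section gives recurrence hazard ratios by metabolic syndrome and testosterone.

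Study aims and design lists tumour markers such as stage, grade and receptors, and then says "we are specifically interested in markers of the host that can be modified through life-style". Under the inclusion criteria and Recruitment, the values needed to classify all three host markers are obtained on every candidate to establish eligibility. The strata in Randomization are age, adjuvant treatment group and nodal status. Control of potential biases adds date of diagnosis. No host marker is a stratum.

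**The concern.** The planned covariates do not stand in for the host markers, because the protocol's own relative risks for insulin and testosterone are already adjusted for stage, ER and PR. The sample size also leans on these markers: Statistical power raises the expected 5-year risk from 20% to 30% by selecting on high insulin and/or testosterone.

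A prognostic baseline variable left out of a Cox model moves the treatment hazard ratio toward 1 and costs some power. A chance imbalance in it is then handled neither by stratification nor by the model. Pre-specified baseline terms are valid in a randomised comparison and need no new data. The question is how much they would bring.

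**Working it through.** **Inputs from the documents.**
- Control risk: "we estimate that about 30% of patients will develop a recurrence or a second primary BC within 5-year follow-up: 360 cases out of 1200".
- Effect: the intervention "will reduce BC recurrence rate by 33% or more, but we consider also a more prudent estimate of 25% reduction". A 25% reduction takes 30% to 22.5%.
- Size: "Our aim is to recruit 1,200 high risk patients in order to have 600 patients per arm".
- Table 1 groups: neither marker, HR 1 (53 women); metabolic syndrome only, 2.2 (4); testosterone only, 3.8 (41); both, 6.7 (12).

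**Step 1: the plan's own figure.** The two-proportion formula is n = [z(α/2)·√(2p̄q̄) + z(β)·√(p₁q₁ + p₂q₂)]² / δ². For 0.30 against 0.225, p̄ = 0.2625 and δ = 0.075. At 80% power and two-sided 0.05:

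n = (1.960 × 0.6222 + 0.8416 × 0.6200)² / 0.005625 = 539.1, so 540.

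The continuity correction, (n/4)·[1 + √(1 + 4/(nδ))]², gives 566, the plan's entry. All eight entries of the sample-size table reproduce this way. The table does not depend on covariates.

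**Step 2: time-to-event equivalent.** Expected events are 600 × (0.30 + 0.225) = 315. The hazard ratio is ln(0.775)/ln(0.70) = 0.715. Power is Φ(√315/2 × |ln 0.715| − 1.96) = 84.7%. The two-proportion formula without correction gives 84.0% at 600 per arm.

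**Step 3: marker spread among eligible women.** The log hazard ratios are 1.335 (41 women), 0.788 (4) and 1.902 (12). Their weighted mean is 1.416, and the standard deviation is √(4.68/57) = 0.29. Table 1 does not classify by insulin, so women eligible on insulin alone sit unseen in its reference group. An assumed insulin-only group of 10 or 20 women per 57, at an assumed HR of 2, gives a standard deviation of 0.37 or 0.40. The whole Table 1 cohort, including the HR 1 group, gives 0.74.

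**Step 4: simulated power with and without the markers.** Each setting has 4,000 trials of 600 per arm with exponential times, censoring at 5 years and no non-compliance. Five-year risks are fixed at 30% and 22.5% averaged over markers. A treatment-only Cox model is compared with one that adds the markers. Simulation error is about 0.6 points on each power; gains were taken before rounding.

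| Setting | SD of log risk | Power without | Power with | Gain (points) |
|---|---|---|---|---|
| Eligible Table 1 groups | 0.29 | 84.5% | 85.2% | 0.7 |
| plus 10 insulin-only (assumed) | 0.37 | 84.3% | 85.9% | 1.5 |
| plus 20 insulin-only (assumed) | 0.40 | 84.3% | 86.2% | 1.9 |
| Whole Table 1 cohort (not the trial population) | 0.74 | 84.8% | 89.4% | 4.5 |
| Continuous score (assumed) | 0.30 | 84.8% | 85.2% | 0.4 |
| Continuous score (assumed) | 0.50 | 84.5% | 87.4% | 2.9 |
| Continuous score (assumed) | 0.70 | 84.2% | 89.1% | 4.9 |
| Continuous score (assumed) | 1.00 | 85.0% | 93.8% | 8.8 |

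In the first three rows the mean hazard ratio is 0.712 to 0.714 without the markers and 0.707 to 0.710 with them. The continuous rows give the model the true score, so each is a best case for its standard deviation.

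**Step 5: chance imbalance.** With a standard deviation of 0.40, the between-arm difference in mean log risk has standard error 0.40 × √(2/600) = 0.023. The log hazard ratio has standard error 2/√315 = 0.113. A typical imbalance is therefore about one fifth of a standard error.

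**The case against.** The strongest objection is that the gain is too small to matter. Entry requires at least one raised marker, which removes much of the low-risk group and narrows the spread. The smallest gain, 0.7 points, is about the size of the simulation error. The comparator was also a treatment-only model, whereas the plan already intends clinical-pathological adjustment. Both points stand, and they limit the claim to a modest improvement.

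A second objection concerns the measurements. The Compliance section notes that adjuvant therapy can change these biomarkers and restricts biomarker comparisons to samples from the same treatment phase. Women may enter at diagnosis or after chemotherapy, so baseline values mix phases. This adds noise to the covariate and may reduce the gain. It does not bias a comparison adjusted for variables measured before randomisation.

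Some stronger readings are tempting but not supported:
- A reader might infer that these are the strongest predictors of recurrence. The documents give no effect size for nodes, stage, grade or receptors, so no ranking is possible. Table 1 has 32 recurrences in 110 women.
- A reader might infer a three-fold spread of risk among eligible women from 6.7/2.2. The 2.2 rests on four women and one recurrence (interval 0.2 to 19.4). The two larger eligible groups give 6.7/3.8 = 1.8, with 7/12 against 17/41 recurrences (Fisher p = 0.34).
- A reader might take the testosterone range of 2 to 7 as ground for a gain of five points or more. That needs a standard deviation of about 0.7, close to the 0.74 of a cohort that includes the HR 1 group.
- A reader might infer that the markers are deliberately excluded. The covariates are unlisted; the markers are simply not named.

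**Conclusion.** The point holds in a limited form. The plan does not name three baseline host markers that its own background treats as prognostic and that are available on every woman before randomisation. The randomised comparison remains unbiased without them. The small difference in hazard ratio arises because the adjusted ratio compares women with the same marker profile, while the unadjusted one averages over profiles.

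The gain in power is about 1 to 2 points. It rests on the Table 1 hazard ratios, which are imprecise, on the assumed size and HR of the insulin-only group at the upper end, on full compliance, and on a treatment-only comparator. It would be about 3 to 5 points if the markers, used as continuous variables, carried a log-risk standard deviation of 0.5 to 0.7, which the documents do not establish for eligible women. The increment over clinical-pathological adjustment cannot be computed from the documents, since they give no hazard ratios for those factors. The case for the change is its very low cost, not the size of the gain.

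**What to change.** In Statistical analysis, state that the primary intention-to-treat Cox model includes baseline log testosterone, baseline log insulin (both continuous) and metabolic syndrome (yes/no). These go alongside the clinical-pathological covariates, named one by one, and the randomisation factors, including adjuvant treatment group.

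The cost is wording, plus three model terms against about 315 expected events. No new measurement is needed. The downside is some noise in the marker terms because baseline samples come from different treatment phases.

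An interaction of arm with baseline testosterone is optional and should be labelled exploratory. Its standard error per standard deviation of the marker is about 2/√315 = 0.113. An assumed interaction of half of |ln 0.75|, that is 0.144, would have power of about Φ(0.144/0.113 − 1.96), roughly 25%.

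### The plan analyses ER, PR and erbB2 groups separately but has no test of whether the intervention effect differs between them

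*Combined protocol and SAP*

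**What the plan says.** The only text on receptor subgroups is one sentence under Statistical analysis: "Separate analyses will be carried out by ER, PR and erbB2 status". The sentence before it gives the estimator: "Hazard ratios and confidence intervals will be computed by the Cox proportional hazard model, with standard clinical-pathological prognostic covariates as potential confounders". Covariates therefore enter as confounders. No arm-by-marker term is mentioned there or anywhere else. The documents also give no exploratory label, no multiplicity rule for these analyses and no rule for reading a difference between strata.

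The main analysis is kept distinct: "The main analysis of the intervention effect on the incidence of recurrences will be by intention to treat".

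The sample size refers to the whole trial. Statistical power states that 600 women per arm is a number "which shall guarantee 80% chance of getting a significant difference also with 25% reduction", and the opening summary says that "the statistical power of the study is 80% or, respectively, 90%, (P<0.05, 5-year follow-up" for reductions of 25% and 33%. No power is given within any receptor group, and no receptor prevalences are given.

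Control of potential biases says that the treatment strata used in randomisation depend partly on hormone receptor status. That helps balance the arms but does not test effect modification, and erbB2 is not mentioned there.

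**The concern.** The usual reason to repeat an analysis by receptor status is to see whether the intervention works differently in the two groups. Separate models give two hazard ratios and no estimate of their ratio. The temptation is then to compare a significant stratum with a non-significant one. That comparison does not test a difference: each stratum has only part of the events, and the smaller one may miss significance for lack of information alone.

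At stake is a report that the intervention works only in, say, ER-positive disease when the effect is the same in all women. If the overall result is null, an isolated significant stratum could be presented as a finding. Because the three markers are named in advance, either result would look prespecified.

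**Working it through.** **Inputs from the documents.** 600 per arm; two-sided 0.05 (the power table is introduced as "two sided, or one sided", with 0.10 for the one-sided option); the intervention "will reduce BC recurrence rate by 33% or more, but we consider also a more prudent estimate of 25% reduction"; and "about 30% of patients will develop a recurrence or a second primary BC within 5-year follow-up: 360 cases out of 1200".

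**Assumed.** Each marker has two levels, giving six strata. Events split between the levels from 50/50 to 85/15. The hazard ratio is identical in both.

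**1. The plan's own figure.** Take 0.30 against 0.225 (mean 0.2625), two-sided 0.05 and 80% power:

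n = [1.96·√(2·0.2625·0.7375) + 0.8416·√(0.30·0.70 + 0.225·0.775)]² / 0.075² = 539.1

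With the continuity correction, n′ = (n/4)·[1 + √(1 + 4/(n·0.075))]² = 565.4, which rounds up to the stated 566. The same method, with one third as the 33% reduction, gives all eight cells of the table. So the sizing is a whole-trial comparison with a control rate of 30%.

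**2. Power within a stratum.** With e events and 1:1 allocation, power = Φ(√(e/4)·|ln HR| − 1.96). For all 360 events at HR 0.75, √90 × 0.2877 = 2.729, so power is Φ(0.769) = 78%.

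**3. Chance that exactly one stratum is significant.** The two strata of a marker contain different women, so this is a(1−b) + b(1−a), where a and b are their powers. At HR 0.75 with 360 events:

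| Split | Events | Power a, b | Exactly one significant |
|---|---|---|---|
| 50/50 | 180, 180 | 49%, 49% | 50% |
| 65/35 | 234, 126 | 60%, 37% | 53% |
| 75/25 | 270, 90 | 66%, 28% | 57% |
| 80/20 | 288, 72 | 69%, 23% | 60% |
| 85/15 | 306, 54 | 71%, 18% | 63% |

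**4. Other readings of the plan's inputs**, from 50/50 to 85/15:

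- 30% as the control rate gives 180 + 135 = 315 events. At HR 0.75 the chance is 49% to 60%. At HR ln(0.775)/ln(0.70) = 0.715 it is 49% to about 66%.
- 33% reduction as HR 0.67 with 360 events: 36% to 66%.
- 33% reduction as 30% against 20%, so 180 + 120 = 300 events and HR ln(0.80)/ln(0.70) = 0.626: 30% to 64%.

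An interaction test at two-sided 0.05 falsely indicates a difference in 5% of trials per marker in all these settings.

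**5. No effect at all.** For one marker, the chance that at least one of its two strata is significant is 1 − 0.95² = 9.75%, against 5% for its interaction test. Across three markers the strata overlap, because each marker divides the same women. Simulation with that overlap, over assumed splits and ER–PR correlations, gives about 20 to 22% for at least one of six. Three interaction tests give about 14% (1 − 0.95³ = 14.3% if independent).

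**The case against.** The plan promises hazard ratios and confidence intervals, sets no significance rule by stratum and announces no receptor-specific claim. Receptor status is not among the aims; Study aims and design lists it only as something to be recorded. A reader might infer that the plan will declare effects stratum by stratum. The documents do not say so, and the figures in steps 3 and 4 apply only under that reading. This part of the objection stands.

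A reader might also take 50 to 63% as the error rate of the planned method. It is not. When both strata truly benefit, the significant one is a correct detection and the other is merely imprecise. Simulated at HR 0.715 with 315 events, the two 95% intervals overlap in about 99% of discordant pairs. The non-significant stratum's interval contains the other's hazard ratio in 69% (50/50), 79% (75/25) and 88% (85/15) of them. Someone who reads the intervals would usually see compatible results. The error arises only if the contrast in significance is taken as evidence of a difference.

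Nor does the null-case figure reach 1 − 0.95⁶ = 26%. That needs six independent tests, which three divisions of the same women cannot supply.

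What survives is that overlapping intervals are not a test of difference either, and the plan offers no other. It defines success for the whole trial as a significant difference, and nothing keeps that habit out of the strata.

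**Conclusion.** The concern holds in this limited form: the plan has separate receptor analyses, no test of effect modification, and a sample size chosen for the whole trial. If strata are compared by significance, an identical effect would look receptor-specific in about 50 to 63% of trials per marker at HR 0.75 with 360 events, and in about 30 to 66% at the 33% reduction. An interaction test would do so in 5%. Under no effect the contrast is about 20 to 22% against about 14%.

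The figures rest on assumed event splits, two levels per marker, the plan's event counts, and no dilution for non-compliance or contamination. The lack of a test does not depend on any of these.

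A reader might infer that the trial's main conclusion is at risk. The documents do not support that: the intention-to-treat analysis, the sample size and the conduct are untouched. This should be corrected before analysis, but it is a secondary matter.

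**What to change.** Keep the stratum hazard ratios and confidence intervals, and label them exploratory. For each marker, add one Cox model in all randomised women with arm, marker, arm-by-marker interaction and the prognostic covariates already planned. If hazards are not proportional between marker groups, stratify the baseline hazard by marker; the marker main effect then drops out and the interaction stays. Report the interaction estimate (the ratio of hazard ratios) with its confidence interval and p-value. Base any claim of a receptor-specific effect on that test, and state that three such tests are made, since together they still carry about a 14% chance of a false positive.

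The cost is a sentence or two and three extra models, with no new patients or data.

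The downside is low power. For a ratio of hazard ratios of 0.75 with 360 events split 50/50, the standard error is √(4/180 + 4/180) = 0.211, so z = 0.2877/0.211 = 1.36 and power is about 28%. At 80/20 it is about 19%. Fewer subgroup claims will be possible, and a non-significant interaction must not be reported as proof that the effect is the same.
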